## Procedures

All participants in both groups will make a total of 3 visits over a 16-week period. The 2nd visit is at week 4 and 3rd visit at week 16 after initial visit. At each visit, all patients will have a blood test for A1c, CMP, CBC, fasting lipid and measurements of body weight, height, blood pressure, and heart rate, answered adverse reaction questions and completed the Diabetes Medications Satisfaction (DM-SAT) Questionnaire form.

At first visit, the following changes will be made in intervention group:

- (1) All prandial insulin injections (Humalog, Novolog, Apidra, Novolin R or Humulin R) will be discontinued.
- (2) Basal insulin (NPH, Lantus, Levemir, Toujeo or Tresiba) will be continued at 80 % of the home dose. The dose will be gradually increased until the patient is back on the home dose (the dose that the patient has been taking at home prior to the enrollment) or fasting BG of 80-130mg/dl was achieved by using the self-titration regimen. (Attachement#1)
- (3) If the patient is on pre-mixed insulin 2-3 times daily, it will be switched to a basal insulin alone and Glargine was given at 40% of total daily dose of pre-mixed insulin. The dose will be gradually increased until fasting BG of 80-130mg/dl is achieved by using the self-titration regimen. (Attachement#1)
- (4) Metformin at home dose will be continued, but other non-insulin diabetes medications will be discontinued. If the patient is not on metformin, then Metformin ER will be started at 500mg daily with a meal for 2 weeks and then 1000mg daily as a maintenance dose if tolerated.
- (5) Both SGLT2i, Empagliflozin 10 mg or 12.5mg once daily, and GLP1 RA, Dulaglutide 0.75mg subcutaneously once weekly, will be added to metformin and a basal insulin.

The patients will be trained on the injection technique of the once-weekly GLP1 RA and given information on potential side effects, risk and benefits of all new medications in detail, hypoglycemia management and the self-titration regimen for the basal insulin.

In the control group, the patients will be advised to remain on MDI and to have the usual and standard care through the primary care provider. They will also be advised to gradually increase the basal insulin until fasting BG of 80-130mg/dl is achieved by using the self-titration regimen as in the intervention group. (Attachement#1)

The patients in both groups will be advised to monitor FPGs daily at minimum.

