A research coordinator will make a phone call to all participants in both groups at week 1, 2, 8, and 12 to review fasting glucose measurements, ask for possible adverse events, incidents of hypoglycemia, and any change in medication.

At each visit, the patients will be questioned for adverse events (nausea, vomiting, diarrhea, headache, acute pancreatitis, bacterial or fungal genito-urinary tract infection, severe hypoglycemia with blood glucose <40, mild hypoglycemia with BG 41-69, diabetes ketoacidosis, any hospitalization for hyper or hyper-glycaemia).

At 2nd visit, Empagliflozin and GLP1 RA, Dulaglutide will be increased to maximum doses of 25mg and 1.5mg respectively if the patient tolerated the starting dose and if the additional glycemic control is required.

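### The visit adverse-event list has no open item and counts only glycaemia-related admissions, so other admissions, unlisted events and drug stops in weeks 12–16 are not prompted for

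*Combined protocol and SAP*

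**What the plan says.** All of this is in the Procedures section of the combined protocol and SAP.

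- **Visits.** "All participants in both groups will make a total of 3 visits over a 16-week period". The second is at week 4, and the third and last is the "visit at week 16 after initial visit".
- **Safety questions at visits.** The section first says only that patients "answered adverse reaction questions and completed the Diabetes Medications Satisfaction (DM-SAT) Questionnaire form", without giving the content of those questions. It later gives a bracketed list: "At each visit, the patients will be questioned for adverse events (nausea, vomiting, diarrhea, headache, acute pancreatitis, bacterial or fungal genito-urinary tract infection", then severe and mild hypoglycaemia, ketoacidosis and, as the last entry, "any hospitalization for hyper or hyper-glycaemia". No word marks the list as examples, and it has no entry for other events, for death, for admission from another cause or for a change in medication.
- **Phone calls.** "A research coordinator will make a phone call to all participants in both groups at week 1, 2, 8, and 12", to review fasting glucose and to "ask for possible adverse events, incidents of hypoglycemia, and any change in medication". No list is attached to that question.

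The documents define no serious adverse event, give no procedure for reporting one, and plan no contact after week 16.

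**The concern.** The less formal contact, the phone call, asks the broader question. The visit, which is the last contact, asks the narrower one. A patient admitted in week 14 for something unrelated to glucose, or who stopped a study drug or insulin in week 13, would reach the final visit without a planned question that covers it.

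Three features of the trial make this worth correcting.

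- The step-down arm has a large change of regimen. Prandial insulin and non-insulin drugs other than metformin are stopped, two agents are added, and metformin is started if the patient is not already on it. The title asks whether this is a better option, and all-cause admissions and drug stops belong to that question.
- The question on medication change appears only in the calls. A stop between weeks 12 and 16 falls just before the primary A1c measurement, and knowing of it would help in reading that value.
- The trial is open-label, and the detailed side-effect counselling on the new drugs is described under the step-down arm. If unlisted events are recorded only when volunteered, reporting could differ between arms. The documents do not show in which direction.

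**Working it through.** No sample size, power or alpha is involved. The check sets each period of follow-up against the contacts that come after it.

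**Inputs (Procedures):** visits at weeks 0, 4 and 16; calls at weeks 1, 2, 8 and 12; follow-up of 16 weeks; open question at calls, printed list at visits.

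| Period (weeks) | First contact afterwards | Question there | Next open question |
|---|---|---|---|
| 0–1 | call, week 1 | open | week 1 |
| 1–2 | call, week 2 | open | week 2 |
| 2–4 | visit, week 4 | list | week 8 |
| 4–8 | call, week 8 | open | week 8 |
| 8–12 | call, week 12 | open | week 12 |
| 12–16 | visit, week 16 | list | none |

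**Period with no later open question:** last visit − last call = 16 − 12 = 4 weeks. As a share of follow-up, 4/16 = 25%.

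**Period where the open question is only delayed:** weeks 2–4, which is 2 weeks. The week-8 call follows, and its question is not restricted to the time since the week-4 visit.

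**What the list covers at week 16.** Acute pancreatitis, ketoacidosis, genito-urinary infection and hypoglycaemia are listed in their own right, whether or not the patient was admitted. The gap is therefore limited to admissions for other causes, serious events not on the list, and drug stops.

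**Exposure in the gap.** The Statistical Analysis section plans 20 patients per arm, 40 in all. 40 × 4 weeks = 160 patient-weeks, and 160/52 ≈ 3.1 patient-years. The documents give no admission rate, so no expected number of missed events can be calculated. One patient with a missed admission is 1/20 = 5 percentage points of an arm.

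**The case against.** **The list may not be exhaustive.** The text does not say that only these events are asked about, and the form behind the adverse-reaction questions is not in the documents. A reader might infer that other serious events in the last four weeks are never asked about. That goes too far: the form may hold an open item, and a patient may volunteer an event. What stands is that the plan as written requires neither an open item nor an all-cause hospital item, and nothing else in it fills the gap.

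**The gap could be drawn too wide.** A reader might add weeks 2–4 to weeks 12–16, giving 6/16 = 37.5% of follow-up. The first of these periods is a delay and not a loss, because the week-8 call can recover it. The same holds for drug stops, since the calls ask about medication changes. At week 4, moreover, the dose decision depends on tolerance of the starting doses, so staff have to establish tolerance in the step-down arm. The lasting gap is weeks 12–16 only.

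**The doses in the gap are unknown.** A reader might infer that most step-down patients will be on raised doses by then. The increase at week 4 depends on both tolerance and need, and the documents give no expected proportion.

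**Other safety data are collected.** Several drug-related harms are on the list, and CMP and CBC are repeated at every visit. This narrows the gap, but a laboratory panel does not record an admission or the reason a drug was stopped.

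**No stated result depends on it.** This is correct. The Outcome measurements section names no adverse-event outcome.

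**Conclusion.** The point holds as a minor one. Visits and calls ask different safety questions, and the narrower one is the only one planned after week 12. Non-glycaemic admissions, other unlisted serious events and drug stops in weeks 12–16, 25% of follow-up, are not prompted for.

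This rests on two assumptions. The first is that the visit questions follow the printed list. If the form already has an open item, an all-cause hospital item and a medication-change item, only the protocol text needs correcting. The second is that the open question at a call reaches back past an intervening visit, so that weeks 2–4 are covered at week 8. The wording allows this.

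A reader might infer that the gap biases the trial's main result. The documents do not support that: A1c is measured regardless of these questions, and no stated primary or secondary outcome uses adverse events or drug stops. What is affected is the completeness of the safety account and the information available for interpreting the week-16 A1c.

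**What to change.** In Procedures, for each visit and in both arms:

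1. Add the open adverse-event question and the medication-change question already used on the calls.
2. Replace the glycaemia-only hospital entry with one for any hospital admission or emergency visit for any reason, recording the cause. This also removes the apparent typing error.

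In Statistical Analysis, say that these events will be listed descriptively by arm, without a formal test. With 20 patients per arm a comparison of admissions would not be informative.

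The cost is two or three lines on an existing form and a few minutes per visit. The change needs no extra visit or blood test and leaves the sample size, the stated outcomes and patient management as they are.

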## Outcome measurements

The primary outcome is the change in A1c at the end of study period at week 16 and secondary outcomes are the changes in fasting blood glucose, weight, blood pressure, heart rate, fasting

lipids, serum sodium and potassium, serum creatinine, liver enzymes, CBC and Diabetes Medications Satisfaction (DM-SAT) scores at week 16.

Treatment satisfaction will be measured using the Diabetes Medication Satisfaction Tool (DM-SAT).

The DM-SAT measures satisfaction with the patient's diabetes medications regimen. The instrument consists of 16 items which create 4 subscales (3 items for wellbeing, 3 items for medical control, 5 items for lifestyle, and 5 items for convenience) and a total score. Responses are summed and converted to a score from 0 to 100 for each subscale and overall, with higher scores representing more satisfaction.

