### **Statistical Analysis:**

We will attempt to recruit and consent 20 patients in each arm that was calculated to provide an 80% statistical power at a 0.05 alpha in this continuous endpoint, two independent sample study.

The calculation was based on the following:

A mean Hemoglobin A1c of  $8.5 \pm 1\%$  at the initiation of the study period. In the treatment group we anticipate a decline in Hemoglobin A1c of 12-15% by the end of the study period. The standard deviation for the mean A1c was derived from the literature (Glucagon-Like Peptide 1 Receptor Agonist or Bolus Insulin With Optimized Basal Insulin in Type 2 Diabetes. Michaela Diamant Et al. Diabetes Care October 2014 vol. 37 no. 10. 2763-2773)

The data will be analyzed by using SPSS or similar software. Significance testing will be conducted at the two-sided 5% level. Continuous variables will be examined for normality and if assumption is met, differences in mean values will be tested using Student's t test an analysis of variance (ANOVA). If not normally distributed, non-parametric procedures will be used, including Wilcoxon rank Sum test. Categorical data will be analyzed using Fisher's exact test and Chi square analysis. Since before/after comparisons will also be performed on the same study patients, we will utilize paired t tests and McNemar's chi-square test.

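### Laboratory variables are planned only as week-16 changes compared by means or ranks; no week-4 or per-patient laboratory analysis is prespecified

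*Combined protocol and SAP*

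**What the plan says.** The Outcome measurements section gives one form and one time point for every secondary variable: "secondary outcomes are the changes in fasting blood glucose, weight, blood pressure, heart rate, fasting" continuing to "lipids, serum sodium and potassium, serum creatinine, liver enzymes, CBC and Diabetes Medications Satisfaction (DM-SAT) scores at week 16". Sodium, potassium, creatinine, liver enzymes and blood count therefore stand in the same list as weight and questionnaire scores.

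The Procedures section collects more than that list uses: "At each visit, all patients will have a blood test for A1c, CMP, CBC, fasting lipid". The visits are at entry, week 4 and week 16, so each patient has two post-baseline samples.

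Under Statistical Analysis, for continuous variables that look normal, "differences in mean values will be tested using Student's t test" or ANOVA; otherwise a Wilcoxon rank-sum test is used. Fisher's exact, chi-square, paired t and McNemar tests are also named, but none is tied to a laboratory variable or to a visit.

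The adverse-event questions in Procedures begin "nausea, vomiting, diarrhea, headache, acute pancreatitis, bacterial or fungal genito-urinary tract infection, severe hypoglycemia with blood glucose <40" and go on to mild hypoglycaemia, ketoacidosis and glycaemia-related hospitalization. They name no renal, electrolyte, liver or blood-count event, and adverse events are not listed as an outcome.

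**The concern.** Laboratory harm usually appears as a few patients with large changes, not as a small shift in everyone. A mean dilutes those patients and a rank test reduces each to one high rank. With the t test, a large outlier also inflates the standard deviation against which it is judged.

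Timing adds a second gap. Week 4 is the first sample after the step-down arm starts its new drugs. The dose increase at that visit applies "if the patient tolerated the starting dose and if the additional glycemic control is required", with no laboratory result mentioned. A change seen at week 4 and gone by week 16 adds nothing to the planned outcome.

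At stake is how the results are read. A row of non-significant week-16 differences could be taken as reassurance when the analysis could hardly have shown anything else. In an open-label trial, whether individual cases are reported would then be a post hoc choice.

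**Working it through.** **The plan's own figure.** The only sample-size figure is 20 per arm, for A1c; none is given for laboratory variables. From the stated inputs (SD 1, decline of 12% of 8.5 = 1.02, two-sided 5%, 80% power), n = 2 × (1.96 + 0.84)² × 1² / 1.02² ≈ 15.1, so 16 per arm, or 17 with the t distribution. The planned 20 is larger, and a dropout allowance of 15 to 20%, which the plan does not state, would explain it. This does not affect the present point; 20 per arm is taken as given.

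**Inputs.** From the documents: 20 per arm, two-sided 5%, t test or rank-sum test, change at week 16. Assumed, because the documents give no figure: SD of creatinine change 0.10 to 0.20 mg/dL; a rise r of 0.5 or 1.0 mg/dL in k = 1 or 2 of the 20 step-down patients; no other difference between arms.

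**Step 1: why the t test cannot see it.** The arm mean moves by kr/20. The expected variance in that arm becomes σ² + r² × k(20 − k)/(20 × 19). The standard error is √(pooled variance × 2/20).

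- k = 1, r = 1.0, σ = 0.10: mean shift 0.05; arm variance 0.01 + 0.05 = 0.06; pooled (0.06 + 0.01)/2 = 0.035; SE √0.0035 = 0.059; t ≈ 0.85.
- k = 2, same r and σ: mean shift 0.10; arm variance 0.01 + 0.0947 = 0.1047; pooled 0.0574; SE 0.0757; t ≈ 1.32.

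The critical value on 38 degrees of freedom is 2.02. A larger rise does not help. As r grows, t tends to (r/20)/(r/20) = 1 for one patient, and to 0.10/√(0.0947/20) = 1.45 for two.

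**Step 2: simulation.** 20,000 trials per row; percentage with p < 0.05.

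| SD | Rise | One patient: t / rank | Two patients: t / rank |
|---|---|---|---|
| 0.10 | 0.5 | 4.5 / 5.0 | 9.0 / 6.6 |
| 0.10 | 1.0 | 1.8 / 5.1 | 5.4 / 6.5 |
| 0.15 | 0.5 | 5.0 / 5.0 | 8.1 / 6.4 |
| 0.15 | 1.0 | 3.5 / 4.6 | 8.5 / 6.8 |
| 0.20 | 0.5 | 5.0 / 4.9 | 7.3 / 6.3 |
| 0.20 | 1.0 | 4.3 / 4.7 | 8.6 / 6.3 |

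With no affected patient both tests reject in about 5%. One affected patient leaves the rate at or below that; two raise it only slightly. Setting the affected values exactly at r, rather than adding r to a random change, gives at most 9.6%. Every setting is non-significant in over 90% of trials.

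**Step 3: the transient case.** A patient abnormal at week 4 and back to baseline at week 16 has a week-16 change of 0.

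**Step 4: what counts would show.** Exact 95% limits: 1/20 = 5% (0.1 to 24.9%); 2/20 = 10% (1.2 to 31.7%); 0/20 has upper limit 1 − 0.025^(1/20) = 16.8%. Fisher's exact test against 0/20: 1 case p = 1.00, 2 cases p = 0.49, 4 cases p = 0.11, 5 cases p = 0.047.

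**The case against.** Four objections deserve weight.

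1. **The t test may not be the test used.** The plan checks normality first. A Shapiro-Wilk test on the affected arm (an assumed choice; the plan names none) rejects in 76 to 89% of trials at SD 0.10 with a 0.5 rise and in 77 to 100% with a 1.0 rise, but in only 14 to 41% for a 0.5 rise at SD 0.15 to 0.20. Large outliers would therefore mostly send the analysis to the rank test. This stands, but the rank test does no better (4.6 to 6.8% in the table).

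2. **Counting does not create power.** Two cases against none gives p = 0.49, and five against none are needed for p < 0.05. A reader might infer that counts would detect harm the planned test misses. They would not; the gain is that cases are displayed with an honest interval.

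3. **There is some cover elsewhere.** A reader might infer that week-4 results are never analysed. The documents do not go that far: before/after and categorical tests are planned without naming a visit, adverse events are asked about at visits and calls, and nothing prevents clinicians from seeing the results or the team from listing them. But no laboratory abnormality is defined for any of these to act on, so the cover is partial and not prespecified.

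4. **The plan claims no safety conclusion.** A reader might infer that its safety conclusion is unsound. No safety objective or laboratory decision rule is stated, so there is no such conclusion to fault. The risk is of a non-significant result being over-read.

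**Conclusion.** The point holds as a gap in prespecified analysis and reporting, not in data collection. The laboratory variables have one outcome form (change) and one time point (week 16). On the assumed SDs and rises, the planned comparison is non-significant in over 90% of trials when one or two of 20 patients have a large creatinine rise, whether by t test or rank test. For the t test, the Step 1 limits do not depend on the assumed SD. A resolved week-4 abnormality falls outside the outcome altogether.

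The simulation covers creatinine only. The dilution argument carries over to the other analytes, but no figures were derived for them. The primary A1c analysis is unaffected. The change is worth making because the stated outcome form would hide individual or transient laboratory harm that the collected data can show.

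**What to change.** Keep the week-16 mean changes and add to the Statistical Analysis section:

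- For sodium, potassium, creatinine or eGFR, liver enzymes and blood count, a by-arm table of each patient's worst post-baseline value (week 4 or 16), shown as a shift from baseline against the laboratory reference range, with counts and exact 95% confidence intervals.
- A listing of patients with abnormal or markedly changed values at either visit. This also covers those already abnormal at baseline, who can worsen without changing category.
- The thresholds, set by the investigators before any results are seen. The eGFR limit of 45 is an entry criterion and should not be the only one: a fall from 46 to 44 would count, and a fall from 100 to 50 would not.
- A sentence stating that a non-significant mean difference is not evidence of laboratory safety.

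The cost is one table and one listing from data already collected, with no new visit or sample. The intervals will be wide, with 0/20 compatible with a true rate up to 17%, and no testing power is gained.

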### **Statistical Analysis:**

We will attempt to recruit and consent 20 patients in each arm that was calculated to provide an 80% statistical power at a 0.05 alpha in this continuous endpoint, two independent sample study.

The calculation was based on the following:

A mean Hemoglobin A1c of  $8.5 \pm 1\%$  at the initiation of the study period. In the treatment group we anticipate a decline in Hemoglobin A1c of 12-15% by the end of the study period. The standard deviation for the mean A1c was derived from the literature (Glucagon-Like Peptide 1 Receptor Agonist or Bolus Insulin With Optimized Basal Insulin in Type 2 Diabetes. Michaela Diamant Et al. Diabetes Care October 2014 vol. 37 no. 10. 2763-2773)

The data will be analyzed by using SPSS or similar software. Significance testing will be conducted at the two-sided 5% level. Continuous variables will be examined for normality and if assumption is met, differences in mean values will be tested using Student's t test an analysis of variance (ANOVA). If not normally distributed, non-parametric procedures will be used, including Wilcoxon rank Sum test. Categorical data will be analyzed using Fisher's exact test and Chi square analysis. Since before/after comparisons will also be performed on the same study patients, we will utilize paired t tests and McNemar's chi-square test.

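### The primary comparison of A1c change does not adjust for baseline A1c; one pre-named ANCOVA would be more precise with data already collected

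*Combined protocol and SAP*

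**What the plan says.** The Outcome measurements section defines the endpoint: "The primary outcome is the change in A1c at the end of study period at week 16".

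The Statistical Analysis section names no method specific to that endpoint. Its general sentence on continuous variables therefore governs it. If a normality check is passed, "differences in mean values will be tested using Student's t test an analysis of variance (ANOVA". If not, "If not normally distributed, non-parametric procedures will be used, including Wilcoxon rank Sum test". The paired t tests mentioned at the end of the section are for before/after comparisons within patients, not between arms. No covariate, ANCOVA or regression model appears anywhere in the document.

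The baseline value is available. The Procedures section states: "At each visit, all patients will have a blood test for A1c", and the first of the three visits is the baseline visit.

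**The concern.** A change score uses the baseline value by subtracting it in full, which amounts to fixing the slope of week-16 on baseline A1c at 1. When the true slope is lower, subtraction over-corrects. Part of the baseline noise stays in the estimate, and so does part of any chance imbalance between the arms. ANCOVA estimates the slope and removes that part.

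With 20 patients per arm, the width of the interval largely determines how informative the result will be. The sample-size paragraph states an anticipated fall only for the treated arm: "In the treatment group we anticipate a decline in Hemoglobin A1c of 12-15% by the end of the study period". It gives no change for the control arm, yet the Procedures section says of control patients: "They will also be advised to gradually increase the basal insulin until fasting BG of 80-130mg/dl is achieved". If their A1c also falls, the true difference is smaller than planned and there is less power to spare.

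A second, smaller matter is that the choice of test waits on a normality check. The rank-sum branch does not itself estimate a mean difference in A1c change, and the plan does not say what estimate would accompany it.

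**Working it through.** **Inputs from the document (Statistical Analysis).** 20 per arm; two-sided 5% level; 80% power; baseline A1c 8.5 with SD 1; decline of 12 to 15% in the treated arm, which is 0.12 × 8.5 = 1.02 to 0.15 × 8.5 = 1.275 points.

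**Assumed, because the document is silent.** Control change 0; baseline-to-week-16 correlation ρ of 0.3, 0.5, 0.7 or 0.9; SD 1 at week 16 as well.

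**The plan's own figure.** With SD 1 and a normal approximation, n per arm = 2(1.96 + 0.842)²/δ². This gives 15.1, so 16 per arm, at 1.02 and 9.7, so 10 per arm, at 1.275. The t test needs 17 and 11. At 20 per arm, t-test power is 88.2% and 97.5%. The stated 20 per arm for 80% power is therefore not reproduced exactly. It would follow from unstated dropout (16/0.80 = 20, or 17/0.85 = 20). That is a separate point and does not affect this one. The stated SD is for A1c itself; no SD of the change is given.

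**Change score against ANCOVA, SD 1 at both times**

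- Var(change) = 2(1 − ρ)
- Residual variance under ANCOVA = 1 − ρ²
- Ratio = (1 + ρ)/2
- CI half-width = t × √(variance × 2/20), with 38 df for the change score and 37 for ANCOVA. The ANCOVA variance is multiplied by 1 + 1/36 for estimating the slope.
- Power is from the noncentral t distribution without that factor; including it lowers the ANCOVA figures by about 1 point at most.

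| ρ | Var(change) | ANCOVA variance | Ratio | CI half-width | Power at 1.02 |
|---|---|---|---|---|---|
| 0.3 | 1.40 | 0.91 | 0.65 | 0.76 → 0.62 | 76 → 91% |
| 0.5 | 1.00 | 0.75 | 0.75 | 0.64 → 0.56 | 88 → 95% |
| 0.7 | 0.60 | 0.51 | 0.85 | 0.50 → 0.46 | 98 → 99% |
| 0.9 | 0.20 | 0.19 | 0.95 | 0.29 → 0.28 | above 99% for both |

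At 1.275 points, power is already at least 91% without adjustment. If control A1c falls by an assumed 0.3 points, the difference is 1.02 − 0.30 = 0.72 and power goes from 47 to 64%, 60 to 73% and 82 to 87% at ρ 0.3, 0.5 and 0.7.

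**Narrower baseline.** Entry requires A1c above 8%. As an illustration, a normal distribution with mean 8.5 and SD 1, cut at 8, has SD 0.697 (variance 0.486). Its mean is 9.01, so it does not match the plan's 8.5. With slope b, Var(change) = (1 − b)² × 0.486 + (1 − b²).

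| b | Var(change) | ANCOVA variance | Ratio | CI half-width | Power at 1.02 |
|---|---|---|---|---|---|
| 0.3 | 1.148 | 0.91 | 0.79 | 0.69 → 0.62 | 83 → 91% |
| 0.5 | 0.872 | 0.75 | 0.86 | 0.60 → 0.56 | 92 → 95% |
| 0.7 | 0.554 | 0.51 | 0.92 | 0.48 → 0.46 | 99 → 99% |

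At b = 0.9 both half-widths are 0.283.

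**Chance imbalance.** The SD of the baseline difference is SD × √(2/20) = 0.316 (SD 1) or 0.220 (SD 0.70). The median absolute difference is 0.6745 times that: 0.21 or 0.15 points. At slope 0.5, half of it passes into the change-score estimate: about 0.11 or 0.07 points, with 95% limits of 0.31 or 0.22. This shows in A1c points the same variability that the variance ratio captures; it is not an additional loss.

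**Simulation.** In 10,000 trials per setting at 1.02 points, power was 76.4 → 90.3%, 88.8 → 95.5% and 98.3 → 99.1% with SD 1. It was 83.9 → 90.3%, 92.0 → 94.6% and 98.8 → 99.1% with the narrower baseline. Type I error was 4.7 to 5.2% for both methods. The change score failed Shapiro-Wilk in at least one arm in 9 to 12% of simulated trials, about what two 5% tests produce by chance.

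**The case against.** The planned test is not wrong. Allocation is randomised 1:1, the change-score t test is unbiased and holds its level, and it matches the stated endpoint. This stands: the point is about efficiency, not validity.

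The SD 1 figures flatter the gain. A normal baseline with mean 8.5 and SD 1 would put about 31% of patients below the entry threshold. With the narrower baseline the CI shrinks by about 10%, 6% and 3%, against 18%, 12% and 6% with SD 1, and nothing is gained at slope 0.9. There, unadjusted power at 1.02 points is also above 80% throughout; with SD 1 it falls short only at ρ = 0.3. This stands too, and is why both settings are shown.

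The 0.3-point control fall is an assumption, and a uniform fall leaves the interval width and the variance ratio unchanged. It only puts the trial on a steeper part of the power curve. With the narrower baseline and the slope cost included, power there goes from 54 to 63%, 66 to 71% and 85 to 87%.

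The normality switch should seldom fire on data like these, and nothing in the plan forbids reporting a mean difference beside a rank-sum p value. The case for a fixed model is therefore clarity, not a frequent failure.

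These objections limit the size of the benefit. None gives a reason to prefer the unadjusted analysis.

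**Conclusion.** The concern holds. The primary between-arm test is valid but leaves baseline A1c unused except by subtraction. Across assumed correlations of 0.3 to 0.7, adjustment removes 15 to 35% of the variance with SD 1 at both times, or 8 to 21% with the narrower baseline, before a slope-estimation cost of about 3%. The gain is worthwhile at low to moderate correlation and negligible near 0.9. The direction is secure; the size depends on a correlation, a week-16 SD and a control-arm change that the documents do not give. The change should be made because it is nearly free in a trial of 40 patients, not because the planned analysis would mislead.

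**What to change.** In the Statistical Analysis section, name one primary analysis: a linear model of week-16 A1c (or change in A1c) on treatment arm with baseline A1c as covariate. Report the adjusted mean difference, its 95% CI and the two-sided p value, whatever a normality pre-test shows. Check the model residuals, and keep the rank-sum test as a sensitivity analysis.

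Use the same baseline-adjusted model for the continuous secondary outcomes. The reasoning carries over, although no gain has been calculated for them.

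The cost is one degree of freedom and a few lines of wording. No further patients, visits or blood tests are needed, and the named software can fit the model.
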